This gives us two equations in two unknowns, and allows us to estimate the true cumulative incidence of both infections  $\pi_Z$ ,  $\pi_D$  from the observed seroprevalences  $p_Z$ ,  $p_D$ .

To bring together cumulative incidence estimates from multiple tests, the above methods for correcting for sensitivity and specificity can be extended to apply to *any number of tests*, and *any number of combinations of tests* (see Appendix 6).

**8.1.3** Proportion of symptomatic infections. For each infection, the denominator is the number of infected women, and numerator is the number of those reporting symptoms (according to pre-specified criteria) who were confirmed by PCR+, IgM+, or rising IgG. Infections which may either be ZIKV or DENV will be tabulated separately. We will investigate whether the proportion of symptomatic infections for each arbovirus is related to seroprevalence of the others.

8.1.4 Seroconversions and incidence of primary infections. The denominator is the number of women who were initially IgG- and who were retested on IgG at a later date. The numerator is the number of these women who were tested IgG+ at some later date. The time at risk is the total time between the first IgG- and either the first IgG+ if there was one, or the time between the first and last IgG- tests. Incidence of primary infection is found by dividing the number of seroconversions by total time at risk.

Once again, both crude and sensitivity-specificity-adjusted estimates will be considered, and separate estimates will be derived if there is more than one IgG test, using a similar format to *Table 5*.

Associations between incidence on one arbovirus and previous infections with the same or other arboviruses will be explored

8.1.5 IgM prevalence. The denominator is the number of women who were ever tested by IgM, and the numerator is the number whose first IgM test was a +ve. Separate analyses will be performed for different IgM tests, or tests on different samples.

Sensitivity and specificity will be taken into account, as above, and so will ZIKV-DENV cross-reactivity, to give adjusted estimates of IgM prevalence for each assay. Associations between IgM prevalence on one arbovirus and previous infections with the same or other arboviruses will be explored.

Author: [name] (UNIVBRIS)

27

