8.1.6 Incidence of primary infections estimated by increase in seroprevalence. If we know or can estimate the cumulative incidence at a starting point T, then cumulative incidence at time t is related to incidence between t and T as follows:

$$\pi(t) = \pi(T) + (1 - \pi(T) \left( 1 - \exp\left( -\sum_{T \le u \le t} \lambda(u) \right) \right)$$

This can be modelled, for example assuming piece-wise constant incidence.

For DENV infection, which has been present for much longer, it may be preferable to model age-and time-specific cumulative incidence:

$$\pi(a,t) = \pi(a,T) + (1-\pi(a,T)\left(1-\exp\left(-\sum_{T \le u \le t} \lambda(a-T+u,u)\right)\right)$$

Using data from pregnant women, we would model incidence from time T and age 16 upwards.

These calculations assume that cumulative incidence can be estimated by adjusting seroprevalence for sensitivity and specificity as shown in *Section 8.1.2* 

8.1.7 Alignment with surveillance data: population estimates of incidence. Once estimates of incidence are available, they can be aligned with surveillance reports to estimate the proportion of incident infections (symptomatic or not) that are reported to the surveillance system. "Alignment" should be interpreted as putting the dates of the tests on the real timescale, so that incidence estimates for ZIKV, DENV, and CHIKV based on ZIKA-VT data can be compared to numbers of cases notified to national or regional surveillance centers, both confirmed and suspected.

If the estimated incidence in some period t is  $\lambda(t)$  and M(t) cases are reported in, say, the population of adult women aged 16-44, over the same time period and from the same area where ZIKA-VT is recruiting, then we can calculate the proportion of all infections that were reported over that time period as :

$$\theta(t) = \frac{M(t)}{N(1 - e^{-\lambda(t)})}$$

Where N is the relevant population size. This quantity can be examined over time to see if it remains relatively stable, and can be used in analyses of test persistence and adjustments for sensitivity and specificity needed to estimate the gestational age of maternal infection and vertical transmission rate (see Sections 5,7).

Further, once an estimate  $\theta(t)$  is available, it can be used to "gross-up" counts M(t), to estimate the true number of infections on a national or regional basis:  $M(t)/\theta(t)$ .

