#### 8.2 Analyses of properties of diagnostic tests

As noted earlier the ZIKA-VT and ZIKA-VID programs are inter-related and the analyses set out in *Section 7.5* will provide the definitive information on the persistence of IgM and other tests.

However, the population epidemiology data collected by ZIKA-VT also provides an opportunity for *supportive* analyses of test persistence, sensitivity and specificity. Results should be compared with the more formal evaluations undertaken as part of ZIKA-VID, which will comprise evidence from published literature as well as findings from *de novo* field work.

8.2.1 Average persistence of IgM. Given estimates of IgM prevalence (section 8.1.5) and incidence of primary infections based on seroconversion (section 8.1.4) or changes in cumulative incidence (section 8.1.6), estimates of the average persistence of IgM can be estimated by dividing IgM prevalence by IgM incidence.

We anticipate that IgM persistence may differ in women with previous ZIKV or DENV infections. If these women can be identified by avidity tests it will be possible to generate separate estimates of average IgM persistence for primary and secondary infections

8.2.2 Sensitivity and cross-reactivity of IgM and IgG tests. Estimates of sensitivity will be available for IgM and IgG tests in women with infections confirmed by PCR, and from cases where tests failed to detect infections in mothers of babies in whom congenital infection is demonstrated.

8.2.3 Specificity of IgM and IgG tests. Specificity of IgG tests can only be estimated in populations which are known to have not been exposed to the infection in question: this means that data collected in ZIKA-VT is not relevant to estimates of IgG specificity. However, IgM specificity can be studied by observing the relationship between the proportion of tests which are positive and the surveillance data over the previous 12 months. IgM persistence is believed to be about 12 weeks on average, so that an IgM+ occurring at a time when surveillance sources indicate there has been no virus circulating for over 4 or 5 months are highly likely to be false positives from a diagnostic point of view, whether due to persistent antibody, cross-reactions, or other factors; although it will be important to be able to rule out foreign travel before making these inferences. Data of this sort will be of great importance in defining the tails of the persistence distributions of IgM tests

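### Section 8.2.1 divides IgM prevalence in all tested women by primary-infection incidence per susceptible woman, so the quotient is not mean IgM persistence

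*SAP*

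**What the plan says.** Section 8.2.1 estimates average IgM persistence from earlier outputs: "estimates of the average persistence of IgM can be estimated by dividing IgM prevalence by IgM incidence". As incidence inputs it names "incidence of primary infections based on seroconversion (section 8.1.4) or changes in cumulative incidence (section 8.1.6").

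- **Prevalence (8.1.5).** "The denominator is the number of women who were ever tested by IgM". The numerator is those positive on their first IgM test. Neither IgG+ women nor IgM from secondary infection is excluded.
- **Incidence by seroconversion (8.1.4).** "The denominator is the number of women who were initially IgG- and who were retested on IgG at a later date". The scale is per time at risk: "Incidence of primary infection is found by dividing the number of seroconversions by total time at risk".
- **Incidence by rising seroprevalence (8.1.6).** This is headed "Incidence of primary infections estimated by increase in seroprevalence". In its formula λ acts on the share 1 − π(T), so λ is again a primary rate per susceptible woman.

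The term IgM incidence, by which 8.2.1 divides, is not defined anywhere. If avidity tests can identify women with previous ZIKV or DENV infection, 8.2.1 also expects "separate estimates of average IgM persistence for primary and secondary infections".

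**The concern.** Prevalence divided by incidence gives mean duration only when both refer to the same women and the same kind of infection, and when incidence is roughly steady. Here the top is per woman tested and counts any IgM, while the bottom is per susceptible woman and counts primary infection only. No section rescales one to match the other.

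Section 8.2 asks for these results to be compared with the ZIKA-VID evaluations, and it calls the Section 7.5 persistence analysis definitive. An artefact in the ratio could be mistaken for a conflict between analyses. Section 8.1 stratifies its analyses by center and season, and Section 10.3 welcomes centers that differ in DENV incidence and seroprevalence. Such centers would give different quotients for the same true persistence, which could pass for a real center effect.

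The secondary-infection estimate has a further gap. Avidity can divide the IgM+ women into primary and secondary, but it supplies no rate at which secondary infections occur.

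**Working it through.** The SAP gives no numerical result for 8.2.1, so there is no figure to reproduce.

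**Inputs**
- True mean persistence of primary IgM, D1 = 12 weeks, in line with the average that 8.2.3 mentions.
- m = immune (IgG+) share. The SAP gives none, so values are assumed.
- λ1 = primary rate per susceptible woman; λ2 and D2 = rate per immune woman and mean duration for secondary infections.
- r = λ2D2 / (λ1D1). The SAP gives none, so values are assumed.
- Constant incidence (assumed).

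**The ratio as written**

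Prevalence over all women: P = (1 − m)λ1D1 + mλ2D2.

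Quotient: P/λ1 = D1[(1 − m) + m·r]. Relative error: m(r − 1).

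| m | r = 0 | r = 0.5 | r = 1 | r = 2 | r = 3 |
|---|---|---|---|---|---|
| 0.2 | 9.6 | 10.8 | 12.0 | 14.4 | 16.8 |
| 0.5 | 6.0 | 9.0 | 12.0 | 18.0 | 24.0 |
| 0.7 | 3.6 | 7.8 | 12.0 | 20.4 | 28.8 |

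(Weeks; the true value is 12 throughout.) For example, at m = 0.5 and r = 3: 12 × (0.5 + 1.5) = 24, an error of 0.5 × 2 = +100%. Reading down the r = 0 column, centers with identical persistence would report 9.6, 6.0 and 3.6 weeks.

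**Simulation.** With 2,000,000 women, λ1 = 0.002 per week (assumed) and m = 0.5, the quotient was 5.91, 8.91, 11.99, 17.54 and 23.34 weeks for r = 0, 0.5, 1, 2 and 3. The values sit slightly below the formula at high r because the formula is a low-rate approximation.

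**The 8.1.6 route.** With π(T) = 0.5 and λ = 0.002 over 20 weeks, π(t) = 0.5 + 0.5(1 − e^(−0.04)) = 0.5196. The absolute change is 0.0196/20 = 0.00098 per woman-week, about half of λ. Dividing an all-women prevalence by λ therefore brings in the same factor as 8.1.4.

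**Matched parts.** Primary IgM+ per woman tested is (1 − m)λ1D1. Divided by λ1(1 − m), it returns D1. In simulation the matched ratio gave 11.6 to 12.1 weeks at m = 0.3, 0.5 and 0.8 for every secondary rate tried.

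**Rescaling alone is not enough.** If all IgM stays in the numerator, P/[λ1(1 − m)] = D1[1 + m·r/(1 − m)]. At m = 0.5 and r = 1 this is 12 × 2 = 24 weeks. Both changes are needed together.

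**The case against.** **One route can be read more kindly.** Section 8.2.1 speaks of changes in cumulative incidence. Taken as the absolute change in π, that is already per woman in the whole population, and the susceptible-share error disappears. This stands as a reading, but 8.1.6 expresses incidence as λ per susceptible, the 8.1.4 route is untouched, and secondary IgM would remain in the numerator.

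**The size and direction are not fixed.** A reader might infer that the estimate is always too short, or wrong by at most the immune share. The documents support neither. A shortfall equal to m is the r = 0 case; the errors cancel at r = 1; above r = 2 the overstatement exceeds m. The tabulated values also rest on assumed seroprevalence and constant incidence, whereas Section 7.5 says incidence changes over time and Section 8.1 says recruitment favours periods of higher incidence. They are illustrations, not the error expected in this study.

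**The secondary estimate is not wholly impossible.** A reader might infer that it can never be formed. A ZIKV IgG- woman with earlier DENV can enter the 8.1.4 denominator, and 8.1.4 says that associations of incidence with previous infection will be explored. Rising IgG titer is already accepted as evidence of infection in 5.1, and the 8.2.1 statement is conditional on avidity. The gap is strict only for same-virus secondary infection, because a woman already IgG+ cannot enter 8.1.4. For infection after a different virus, 8.2.1 does not call for a stratified rate.

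**The consequence is limited.** Section 8.2 labels these analyses supportive, and no section feeds this ratio into the vertical transmission rate or gestational age at infection.

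**Conclusion.** Wrong as written. The stated division does not give mean IgM persistence unless secondary IgM happens to offset the susceptible share exactly. At constant incidence the relative error is m(r − 1); with a true 12 weeks and an assumed m of 0.5 the result runs from 6 weeks at r = 0 to 24 weeks at r = 3. The SAP estimates no r, so neither size nor sign can be known in advance, and centers with different seroprevalence would differ for the same true persistence (except at r = 1).

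Separately, Section 8.1 defines no incidence of same-virus secondary infection, so the secondary estimate lacks a defined denominator for those women.

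The mismatch follows from the SAP's own definitions; the sizes rest on the assumed m, r and steady incidence. Because the analysis is supportive to Section 7.5, any effect on the vertical transmission rate is indirect.

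**What to change.** In 8.2.1:

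1. Replace the undefined IgM incidence by primary infections per woman tested, λ(1 − π), with π from 8.1.2. The absolute change in π per unit time from 8.1.6 is equivalent.
2. Restrict the numerator to primary (low-avidity) IgM+ women, per woman tested. Make this change together with the first.
3. State that the ratio assumes roughly constant incidence over the IgM window.
4. Define an incidence of secondary infection, for example from IgG titer rises in initially IgG+ women, or drop the secondary estimate.

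Do not match the parts by restricting to women who were IgG- at a preceding test. Infection time is then limited to the gap since that test, and the ratio covers only that part of the persistence curve. Assuming exponential persistence with mean 12 weeks, a 12-week gap gives 12(1 − e^(−1)) = 7.6 weeks.

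The cost is SAP wording. The primary estimate needs no new data collection if avidity testing goes ahead as 7.5.2 foresees. Intervals widen slightly from uncertainty in π and in the avidity classification.

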#### 5.4 Taking test sensitivity, specificity and cross-reactivity into account

PCR tests can be regarded as effectively 100% specific, but they have a short detection window, which varies between individuals. We refer to this as the test's persistence distribution. Serological tests vary in their specificity and sensitivity. Failures of specificity (false positives) can arise for several reasons. While some may be due to a random signal that has exceeded the test's threshold, other false positives may be due to cross-reaction to antibodies to related viruses. Currently available DENV and ZIKV IgM tests react to each other's IgM, and to other flavivirus IgM. We can therefore anticipate that ZIKV and DENV IgM test specificity might vary between collaborating centers, reflecting the geographical distribution of other viruses to which they are cross-reactive. In addition, although IgM antibody is usually assumed to persist for 12 weeks, in some individuals it may persist for many months. Therefore, if IgM is due to an infection acquired many months before the pregnancy, we might regard it as an *analytic* true positive, but a *diagnostic* false positive.

Information on the effective sensitivity and specificity of IgG and IgM assays in different centers is currently incomplete, but will be systematically developed under the ZIKA-VID program. Sources of data on properties of diagnostic tests, for use in ZIKA-VT data analyses, will be updated regularly (see *Appendices 3 & 4*).

Reliable estimates of the sensitivity and specificity of each individual test are not, by themselves, enough to determine the probability that a woman has experienced an infection in pregnancy given her test results. Each woman will be tested on multiple occasions, and on multiple tests. Interpretation of these sequences of tests is complex as we can anticipate there are strong correlations, conditional on true infection status, both between tests results at the same time, and between tests of the same type over time. Rules for determining whether a sequence of tests and clinical findings should be considered as a reflecting a "confirmed", "definite" or "possible" maternal infection will be drawn up by the Expert Diagnostics Group (*Appendix 1*).

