#### 7.5.3 Estimating the persistence distributions of multiple tests

The ZIKA-VT protocol provides for

Author: [name] (UNIVBRIS)

23

- (i) PCR, IgM, and IgG tests on women with symptoms,
- (ii) PCR on all IgM+, IgG seroconversions, and rises in IgG titer.
- (iii) Repeat PCR, IgM, and IgG tests at the prescribed intervals until a first PCR-, IgM-, IgG falling titer, respectively.
- (iv) Use of serum, saliva, and urine samples.
- (v) Avidity tests may be used to determine if an infection is primary or secondary; this also carries information on timing of infection

Thus, each woman's record is likely to consist of a series of results on at least three tests and possibly more if more than one assay of each type is used.

The analysis above for a single test is readily extended to two or more tests k=1,2...K. The data on each individual i now consists of K sets of implied -++- sequences denoted  $U_{Li_k}, U_{Ri_k}, W_{Li_k}, W_{Ri_k}$ , and the parameter set is expanded to accommodate K distributions  $F_k(d,\theta_k)$ . The likelihood for the persistence tests for woman i is then:

$$\Pr\left(\begin{array}{c} (U_{Li_{k}}, U_{Ri_{k}}, W_{Li_{k}}, W_{Ri_{k}}) \mid \pi_{i}(t), \theta_{k} \end{array}\right) = \sum_{t} \pi_{i}(t) \prod_{k} \left( F_{k}(W_{Ri_{k}} - t - 1, \theta_{k}) - F_{k}(W_{Li_{k}} - t - 1, \theta_{k}) \right) \quad Max_{k}(U_{Li_{k}}) \leq t \leq Min_{k}(U_{Ri_{k}})$$

Note that, in this framework, the date of symptoms and the dates of short persistence tests such as PCR, are highly informative about the persistence distributions of longer persistence tests such as IgM and rising IgG.

Extension to multiple tests, use of a variety of tests, and changes in which tests are used, raises questions about the numbers of parameters that may need to be estimated. Our initial strategy will be to assume that the persistence distributions of all tests of the same type (PCR, IgM, rising IgG) have the same underlying parametric or semi-parametric form, with persistence distributions that differ only by a single parameter, for example based on a proportional hazards assumption. This constant would be estimated from the data. Persistence distributions for different *samples* (serum, saliva, urine) on the same test will be treated the same way.

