## 7.6 Accounting for imperfect test sensitivity and specificity, and cross-reactivity

As noted earlier, we need to calculate for each woman recruited into ZIKA-VT, the probability that she was infected in pregnancy, and the distribution of GA when this infection occurred, if it occurred at all, based on tests with imperfect accuracy.

Author: [name] (UNIVBRIS)

24

For example, a sequence of four ZIKV IgM- results throughout pregnancy, assuming there were no IgG, PCR tests and no symptoms, would be scored as "No evidence of maternal infection in pregnancy" in basic analyses, but there is a possibility that they are all false -ves.

As long as the testing algorithm is relatively sensitive, say 95% or more, the bias in estimates of the vertical transmission due to false -ves is likely to be negligible. A small proportion (<5%) of maternal infections would be missed from the denominator, but their babies will not be followed up, and so would also be missed from the numerator. The exception to this would be if they are not only congenitally infected but their congenital infection is apparent. But it can be shown that, on current evidence, this would lead to only a very slight over-estimation of the VTR.

The difficulties posed by false *positive* IgM tests are, however, far more serious. If the specificity of an IgM test is 95%, then 5% of uninfected mothers will receive false +ve results, and will be considered infected in pregnancy. If 10% of women are infected in pregnancy, then, for every 15 women considered as infected in pregnancy, only (approximately) 10 would be truly infected, and the vertical infection rate will be underestimated by a factor of 1.5. If incidence is lower, and only 1% of women are infected in pregnancy, then only 1 in 5 women being followed are truly infected and the vertical transmission rate will be underestimated by a factor of 5.

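### Section 8.2.2 estimates IgM and IgG sensitivity partly in women who reached PCR only through positive serology, and partly from test failures with no denominator

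*SAP*

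**What the plan says.** Section 8.2.2 names two sources for sensitivity. The first is PCR-confirmed women: "Estimates of sensitivity will be available for IgM and IgG tests in women with infections confirmed by PCR". The second is information "from cases where tests failed to detect infections in mothers of babies in whom congenital infection is demonstrated".

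Section 7.5.3 sets out who has PCR. One route is "PCR, IgM, and IgG tests on women with symptoms", which does not depend on serology. The other is "PCR on all IgM+, IgG seroconversions, and rises in IgG titer", which does.

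Three other statements bear on the point:

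- Section 5.4 says of PCR tests that "they have a short detection window, which varies between individuals".
- Section 5.4 also says of results from different tests, and of repeated results from one test, that "we can anticipate there are strong correlations, conditional on true infection status".
- Section 7.6 says of infected women missed by the algorithm that "their babies will not be followed up, and so would also be missed from the numerator".

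Section 8.2 calls its analyses supportive and has them compared with ZIKA-VID. Section 8.2.2 states no restriction by route to PCR, no sample timing, no denominator for the second source and no correction. Section 8.2.3, by contrast, does ask which populations can validly inform IgG specificity.

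**The concern.** A reference group for sensitivity should be assembled without regard to the test being evaluated. Here an infected woman with no symptoms, a negative IgM and no IgG change has no route to field PCR, so she cannot enter the group. Her false negatives are absent from the denominator, and sensitivity is overstated in the part of the group that entered through serology.

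The second source has a different fault. It is described only by its failures, so no proportion can be formed until a denominator is named.

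An overstated sensitivity would understate missed maternal infections. If it reached the adjustments in Sections 8.1.2 and 8.1.5 or Appendix 6, it would also lower the adjusted prevalence.

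**Working it through.** Section 8.2.2 gives no figure to reproduce. The entry routes come from Section 7.5.3. All numerical inputs below are assumptions, because the documents give none.

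**Source 1: PCR-confirmed women, IgM sensitivity**

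- Se = true IgM sensitivity = 0.80
- s = share of infections that are symptomatic = 0.2 (0.5 as an alternative)
- q = PCR+ share in symptomatic infections = 0.7
- p = PCR+ share in serology-triggered samples from women without symptoms = 0.1, 0.3 or 0.6
- T = probability that an infected woman without symptoms triggers PCR

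Apparent Se = [s·q·Se + (1−s)·p·Se] / [s·q + (1−s)·p·T]

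T depends on how IgM and IgG are related given infection:

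- independent, IgG sensitivity 0.9: T = 1 − 0.2 × 0.1 = 0.98
- independent, IgG sensitivity 0.5: T = 1 − 0.2 × 0.5 = 0.90
- IgM in effect the only trigger: T = 0.80

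At s = 0.2 the numerator is 0.112 + 0.64p, which is 0.176, 0.304 and 0.496 for the three values of p. The denominator is 0.14 + 0.8·p·T.

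| Trigger | p = 0.1 | p = 0.3 | p = 0.6 |
|---|---|---|---|
| IgG independent, 0.9 | 0.176/0.2184 = 0.806 | 0.304/0.3752 = 0.810 | 0.496/0.6104 = 0.813 |
| IgG independent, 0.5 | 0.176/0.212 = 0.830 | 0.304/0.356 = 0.854 | 0.496/0.572 = 0.867 |
| IgM only | 0.176/0.204 = 0.863 | 0.304/0.332 = 0.916 | 0.496/0.524 = 0.947 |

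At s = 0.5 the IgM-only row becomes 0.32/0.39 = 0.821, 0.40/0.47 = 0.851 and 0.52/0.59 = 0.881. With symptomatic women only (s = 1) the result is the true 0.80.

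Among women without symptoms alone, apparent IgM sensitivity is Se/T: 0.80/0.98 = 0.816, 0.80/0.90 = 0.889, or 1.000 if IgM is the only trigger. The proportion with any positive serology is 100% in all three cases.

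**Timing of the scored sample.** Suppose IgM is read too early in symptomatic women, with an assumed sensitivity of 0.5 at that time. At s = 0.2 the first numerator term falls from 0.112 to 0.07. The result then runs from (0.07 + 0.064)/0.2184 = 0.614 (independent IgG at 0.9, p = 0.1) to (0.07 + 0.384)/0.524 = 0.866 (IgM only, p = 0.6). Early sampling can therefore make the net bias downward.

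**Source 2: mothers of infected babies.** Take all such mothers as the denominator, and let a be the share of missed mothers' infected babies whose infection comes to light. Then apparent Se = Se / [Se + (1−Se)·a]. With Se = 0.80:

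- a = 0.05: 0.80/0.81 = 0.988
- a = 0.10: 0.80/0.82 = 0.976
- a = 0.30: 0.80/0.86 = 0.930
- a = 1: 0.800

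**Effect downstream.** The relationship in Section 8.1.2 gives adjusted prevalence = (observed − (1−Sp)) / (Se + Sp − 1); Section 8.1.5 applies the same kind of adjustment to IgM. Assume Sp = 0.95 and that the biased value is used in full. The adjusted prevalence is then multiplied by 0.75/(apparent Se − 0.05):

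- apparent Se 0.81: 0.75/0.76 = 0.99
- apparent Se 0.92: 0.75/0.87 = 0.86, about 14% too low
- apparent Se 0.95: 0.75/0.90 = 0.83, about 17% too low

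**The case against.** A reader might infer that both groups were selected by the test result, so that sensitivity is driven to 100% in one and to 0% in the other. The documents do not support that.

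- **Symptomatic women.** They have PCR whatever their serology. Because the PCR window is short, they may form much of the PCR+ group. This stands: only part of the group is affected.
- **IgG triggers.** An IgM- woman can reach PCR through IgG, so IgM sensitivity among women without symptoms is not necessarily 100%. With independent IgG at 0.9 nearly all the inflation disappears. This stands as a limit on size, though the strong correlations expected in Section 5.4 move the answer back towards the higher figures.
- **Stored samples.** Section 1.2 and Appendix 1 foresee further tests before the final analysis. PCR regardless of serology is not excluded, but neither is it planned.
- **Failures only.** Reading the second source as none detected out of all failures is too literal. With a sensible denominator the bias is upward. It is lessened because a birth cohort of mothers without infection is followed (Sections 3.1 and 5.2), so some babies of missed mothers are seen.
- **Supportive status.** Section 8.2 is supportive, and Section 8.1.2 and Appendix 6 take sensitivity from ZIKA-VID. This limits the impact but does not remove it: Section 3.2 says ZIKA-VT information contributes to the ZIKA-VID evaluation, so the comparison is not fully independent.
- **The 95% condition in Section 7.6.** It concerns the whole algorithm. An inflated single-assay figure does not by itself confirm it.

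**Conclusion.** The point holds in a limited form. Following Section 8.2.2 as written builds uncorrected partial-verification bias into the part of the reference group that entered through serology, unless stored samples are later PCR-tested regardless of serology. The second source lacks a denominator and, given the natural one, is also likely to be biased upward.

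The size is open. For a true IgM sensitivity of 0.80 with 20% symptomatic, the verification bias alone gives about 0.81 under an independent IgG trigger of sensitivity 0.9 and 0.86 to 0.95 when IgM is in effect the only trigger. The net direction for the whole group is not certain, because IgM read too early in symptomatic women pulls the other way. The route into the adjusted estimates is indirect, through ZIKA-VID. The text should be corrected, but the documents do not show that the main results are wrong.

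**What to change.** Amend Section 8.2.2 as follows.

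1. Take the main estimate from women whose PCR was triggered by symptoms, or done on stored samples regardless of serology. Score IgM and IgG from a stated later sample, whatever its result. Exclude women who would not have had PCR but for the assay being evaluated, or apply a verification-bias correction. Define the exclusion by route to PCR, not by test result: dropping every IgM+ woman would leave only IgM- women.
2. For the second source, use as denominator all mothers of laboratory-confirmed congenitally infected infants who have IgM or IgG results. State how infants of test-negative mothers are ascertained, and report the estimate as likely biased upward unless infants are tested regardless of the mother's result.
3. Report IgM sensitivity among IgG seroconverters, IgM+ and IgM- alike, as secondary only, because the two tests are expected to be correlated.

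This needs SAP wording and no new samples, unless the stored-sample option is chosen. The cost is fewer women, a wider interval and an estimate that mainly reflects symptomatic infection. That last limit should be stated, since Section 7.5.2 already treats symptoms as a possible influence on persistence.
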